7.5.2.1 Liver Function Tests

The number and percentage of subjects with potentially clinically significant values in liver function tests will be presented.

For LFT changes, study drug dosing should be interrupted if a subject experiences clinically significant liver toxicity related to study drug (\geq Baseline + 4 x ULN to $<$ 20 x ULN for AST and ALT; grade 3 total bilirubin [TBL]). Clinically significant values in liver function tests leading to interrupt dosing will be summarized.

7.5.3 Vital Signs

Vital signs (systolic blood pressure, diastolic blood pressure, body temperature, weight and pulse rate) will be summarized using n, mean, standard deviation, minimum, maximum and median by visit. Additionally, a within-subject change will be calculated as the post-baseline measurement minus the baseline measurement and summarized by visit.

The number and proportion of patients experiencing potentially clinically significant abnormalities during the treatment-emergent period will be summarized. The definition of potentially clinically significant abnormalities are provided in the Table below.

Parameter	Criteria for Potentially Clinically Significant Abnormalities
Systolic blood pressure	Absolute result > 180 mm Hg and increase from baseline > 40 mm Hg
	Absolute result < 90 mm Hg and decrease from baseline > 30 mm Hg
	Final visit or 2 consecutive visits results \geq 20 mm Hg change from baseline
	Most extreme postbaseline result \geq 140 mm Hg
	Most extreme postbaseline result \geq 180 mm Hg
	Most extreme result \geq 180 mm Hg and \geq 20 mm Hg change from baseline
	Most extreme result \geq 140 mm Hg and \geq 20 mm Hg change from baseline
Diastolic blood pressure	Absolute result > 105 mm Hg and increase from baseline > 30 mm Hg
	Absolute result < 50 mm Hg and decrease from baseline > 20 mm Hg
	Final visit or 2 consecutive visits results \geq 15 mm Hg change from baseline
	Most extreme post-baseline result \geq 90 mm Hg
	Most extreme post-baseline result \geq 105 mm Hg
	Most extreme result \geq 105 mm Hg and \geq 15 mm Hg change from baseline
	Most extreme result \geq 90 mm Hg and \geq 15 mm Hg change from baseline
Heart Rate	Absolute result > 120 bpm and increase from baseline > 30 bpm
	Absolute result < 50 bpm and decrease from baseline > 20 bpm

bpm, beats per minute; mm Hg, millimeters of mercury.

7.5.4 Electrocardiograms (ECGs)

Number and percent of subjects with normal, not clinically significant abnormal, and clinically significant abnormal results for the 12-lead ECG will be summarized by treatment group and time point.

Continuous ECG parameters, such as heart rate, PR, QRS, QT and RR, will be summarized by treatment group and time point.

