5.4.6 Electrocardiogram (ECG)

A 12-lead ECG will be performed on all subjects at the Institution and interpreted by the Institution's medically trained staff. Parameters that include heart rate, PR interval, RR interval, QRS interval, QT interval will be collected. Abnormalities and clinical significance as judged by the Investigator will be reported as well. It is recommended that ECG reports are printed in duplicate and photocopied to prevent fading.

ECG should be obtained after the subject has rested quietly and is awake in a fully supine position or semi-recumbent, if supine not tolerated) for 10 minutes.

All on-treatment ECGs will be obtained prior to drug administration. Whenever a study procedure coincides with the scheduled time point for an ECG, the study activities are ideally undertaken in a fixed sequence: ECG first, vital signs.

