7.5.5 ECGs

The 12-lead ECG results will be summarized by treatment group and time point. Abnormalities and clinical significance as judged by the Investigator will be reported as well.

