3.3 Randomization

Subjects who meet the inclusion/exclusion criteria will be randomly assigned to receive enzalutamide or placebo using a 2:1 randomization schedule, with two-third of the subjects being randomized to the enzalutamide treatment group and the other one-third of the subjects being randomized to the placebo group. Subjects randomization will be stratified by two primary regions (Asia versus Other), and ECOG performance status (0 versus 1).

Randomization will be performed via an Interactive Response Technology (IRT).

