6.2.4 Electrocardiogram (ECG)

A 12-lead ECG will be performed and parameters that include heart rate, PR interval, RR interval, QRS interval, QT interval will be collected.

Abnormalities and clinical significance as judged by the Investigator will be reported as well.

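### SAP 7.5.4 names QT but no heart-rate-corrected QT, so a heart-rate change that differs between arms, or occurs within an arm over time, could mask or mimic a QT effect

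*SAP*

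**What the plan says.** Protocol 5.4.6 sets the data collection: "Parameters that include heart rate, PR interval, RR interval, QRS interval, QT interval will be collected". SAP 6.2.4 repeats the same five parameters and defines no derived variable.

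For analysis, Protocol 7.5.5 says only that "The 12-lead ECG results will be summarized by treatment group and time point". SAP 7.5.4 gives two outputs. The first is categorical: "Number and percent of subjects with normal, not clinically significant abnormal, and clinically significant abnormal results for the 12-lead ECG", by arm and time point. The second is quantitative: "Continuous ECG parameters, such as heart rate, PR, QRS, QT and RR, will be summarized", again by arm and time point.

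Protocol Table 1 schedules ECGs at screening, Week 13 and end of treatment, with optional unscheduled recordings. SAP 7.10.4 defines an ECG baseline window (study day 1 or earlier), but SAP 7.5.4 uses no change from that baseline. By contrast, change from baseline is planned for laboratory values (SAP 7.5.2) and vital signs (SAP 7.5.3).

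**The concern.** The QT interval depends on heart rate as well as on repolarisation, which is why it is normally corrected before it is compared across people or over time. The variable needed for the correction, RR, is recorded here with QT, yet the only QT measure named for the table is the uncorrected one.

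The 12-lead ECG is a named safety variable (SAP 6.2), and safety in advanced hepatocellular carcinoma is a secondary objective. If heart rate moves differently in the two arms, the raw QT comparison mixes that movement with any drug effect on repolarisation. A reader following one arm from baseline to Week 13 or end of treatment faces the same problem. What is at stake is how the QT table can be read, not any efficacy conclusion.

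**Working it through.** The documents give no QT, QTc or heart-rate figure to reproduce. The check therefore has two parts: whether a correction appears anywhere in the text, and how large the heart-rate effect would be under stated assumptions.

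**1. Search of the text.** The ECG-related text is in Protocol 1.2.1.1, 5.4.6 and 7.5.5 and SAP 6.2.4, 7.5.4 and 7.10.4. None of these names QTc, Fridericia, Bazett, a QTc threshold or an ECG change from baseline.

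**2. Raw QT with no true effect.** Fridericia's correction is QTcF = QT / RR^(1/3). With RR = 60/HR seconds, QT = QTcF × (60/HR)^(1/3). The inputs are assumptions, not taken from the documents: QTcF 400 or 420 ms, starting heart rate 70 or 75 bpm, change of ±5 or ±10 bpm.

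Example: 420 × (60/70)^(1/3) = 399.0 ms and 420 × (60/80)^(1/3) = 381.6 ms, a shift of −17.4 ms at constant QTcF.

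| QTcF (ms) | Start HR (bpm) | Start QT (ms) | −10 bpm | −5 bpm | +5 bpm | +10 bpm |
|---|---|---|---|---|---|---|
| 400 | 70 | 380.0 | +20.0 | +9.5 | −8.6 | −16.5 |
| 400 | 75 | 371.3 | +18.1 | +8.6 | −7.9 | −15.2 |
| 420 | 70 | 399.0 | +21.0 | +10.0 | −9.1 | −17.4 |
| 420 | 75 | 389.9 | +19.0 | +9.1 | −8.3 | −15.9 |

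A 5 bpm change moves raw QT by about 8 to 10 ms, and a 10 bpm change by about 15 to 21 ms. Under Bazett's square-root relation the ranges are about 11 to 15 ms and 22 to 31 ms, so the choice of formula matters and should be fixed in advance.

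**3. A change in one arm only.** Suppose enzalutamide truly adds 10 ms to QTcF (400 to 410 ms) at 70 bpm. The heart-rate rise d that hides this completely solves 410 × (60/(70+d))^(1/3) = 400 × (60/70)^(1/3). Hence d = 70 × [(410/400)^3 − 1] = 5.4 bpm. Conversely, with no true effect, a 5 bpm fall in that arm alone gives an apparent lengthening of 9.5 ms.

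**4. A change common to both arms.** With the same true 10 ms effect, the between-arm difference in raw QT is 10 × (60/HR)^(1/3):

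- no shift (70 bpm): 9.5 ms
- both arms −5 bpm: 9.7 ms
- both arms +5 bpm: 9.3 ms
- both arms +10 bpm: 9.1 ms

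The comparison with placebo is almost unchanged. The problem is confined to differential change and to within-arm readings over time.

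**The case against.** The strongest reply is that the table is not read alone or without a control. Subjects are "randomly assigned to receive enzalutamide or placebo using a 2:1 randomization schedule", and ECG results are shown by arm. Worsening liver disease can be expected in both arms, and step 4 shows that a shared heart-rate shift barely affects the comparison. Nothing in the documents suggests that enzalutamide changes heart rate. A reader might infer that any heart-rate change would distort the QT result; that does not follow in a placebo-controlled comparison.

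A reader might also infer that the SAP restricts the summary to uncorrected QT. It does not: the list in SAP 7.5.4 is introduced as examples, and table formats are left to TLF specifications that are not among the documents. The text shows that a corrected QT is not named, not that it is excluded.

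Nor does it follow that the planned ECG outputs are uninformative about QT safety. Heart rate and RR are summarised beside QT. Pulse rate and its within-subject change are summarised by visit (SAP 7.5.3). The investigator's reading is tabulated, and clinically significant abnormalities are to be recorded as adverse events (Protocol 5.5.1). A differential heart-rate shift would probably be visible. Protocol 1.2.1.1 also reports that existing data do not suggest a QT risk with enzalutamide.

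All of this stands and limits the point. It does not remove it. Separate arm summaries of QT and RR do not give each subject's corrected QT, its change from baseline or its spread, and a normal/abnormal category is not a quantitative comparison. An open list fixes neither the formula nor the change-from-baseline analysis.

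**Conclusion.** The point holds as a small specification gap. SAP 7.5.4 names uncorrected QT, no readable text specifies a corrected QT or an ECG change from baseline, and the data for both are already collected. A heart-rate difference between arms of about 5 bpm would be enough to hide or create a raw QT difference of roughly 10 ms, on the assumption of a QTcF near 400 ms and a heart rate near 70 bpm. These are illustrations of sensitivity, not estimates of the error expected in this trial, for which the documents give no heart-rate or QT data.

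Materiality is low. The output is descriptive, the documents report no prior QT signal, and the primary overall survival analysis is untouched. Because QT and RR are retained, a corrected value can be derived at any time.

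**What to change.** In SAP 7.5.4, derive QTcF = QT / RR^(1/3), with RR in seconds, for each ECG. Summarise QTcF and its change from baseline by treatment group and time point beside raw QT, using the ECG baseline window already defined in SAP 7.10.4.

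The cost is one derived variable and its summary table, with no new procedure or data collection. Protocol Appendix 12.9 shows that the primary analysis has already been reported, so this can be a supplementary output, with the addition explained in the clinical study report as SAP section 1 requires for changes to planned analyses. Because recordings are few and are made and read locally (Protocol 5.4.6), the corrected summary would be easier to interpret but would not be a definitive QT assessment.

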7.5.5 Other Safety-Related Observations

7.5.5.1 ECOG

Summary statistics and the shift table for ECOG from baseline to post-baseline visits will be provided by treatment group.

7.6 Analysis of Pharmacokinetics

[figure not shown]
[figure not shown]
Pharmacokinetic analyses will be conducted using the PKAS.

Individual and summary tables of plasma concentration of enzalutamide and N-desmethyl enzalutamide and a listing of blood collection times and concentrations will be provided. Summary statistics will be provided including n, mean, standard deviation (SD), geometric mean, minimum, median, maximum, and %CV. Values below the lower limit of quantification (BLOQ) will be set to not be calculated if all values are BLOQ. In cases where

more than half of the individual data in a group are BLOQ, SD and %CV will not be calculated. If one or more values are BLOQ, the geometric mean will not be calculated. Additional model-based analyses may be performed and will be described in a separate population PK analysis plan.

For analysis of PK data, only samples for which the time of sampling relative to the dose and the exact dose is known will be included.

7.7

7.8 Subgroups of Interest

The same analysis of the primary endpoint as described in Section [7.4.1](#) will be conducted separately, using the following subgroups:

- Region (Asia vs Other)
- Baseline ECOG status (0 vs 1)
- AR, defined as Ventana Total AR Nuclear %, (<10% ; AR>=10% ; AR>=30% ; AR>=50%; AR>=80%)
- Age (<65 vs >=65)
- Gender (Male vs Female)
- Number of prior lines (1; >=2)
- Alpha fetoprotein (<= 400 ug/L ; >400 ug/L) at baseline
- Medical history (HBV, HCV, or non-viral)

- HepB surface antigen (positive, negative)
- HCV antibody (positive, negative)
- Patients with medical history of HBV (HBV positive) , examine AR <10% and
≥10%
- Patients with medical history of HCV (HCV positive) , examine AR <10% and
≥10%

Results will be presented as forest plots.

7.9 Interim Analysis (and Early Discontinuation of the Clinical Study)

There is no planned interim analysis; however, unblinded safety data will be evaluated by an independent DSMB. Further safety reviews and details on the process and methods of the safety data review will be provided in the DSMB Charter.

7.10 Handling of Missing Data, Outliers, Visit Windows, and Other Information

As a general principle, no imputation of missing data will be done. Exceptions are the start and stop dates of AEs and concomitant medication. The imputed dates will be used to allocate the concomitant medication and AEs to a treatment period, in addition to determining whether an AE is/is not treatment emergent. Listings of the AEs and concomitant medications will present the actual partial dates; imputed dates will not be shown.

7.10.1 Missing Data

Subjects who do not satisfy the criteria to be counted as responders or have insufficient data to determine or confirm a response per the RECIST 1.1 Criteria will be considered as non-responders in the primary final analysis of response rates. No imputation of data will be done to determine individual subject response.

For continuous variables (e.g., clinical laboratory measurement, vital signs), subjects with missing baseline variable will be excluded from the analysis of change from baseline.

Visit-by-visit analyses of data will exclude subjects who did not provide data at the visit in question. For visit by visit summary of ECOG, no imputation will be made.

Adverse events with missing grade will be displayed as “Missing”, no imputation will be made.

For all analyses other than PK analysis, all values will be included in the analyses.

7.10.2 Missing Dates

As a general rule, the worst case scenario imputation rule is used. Completely missing dates will not be imputed.

To calculate Time from initial diagnosis, 1st day of the Month will be used when Month and Year are available; and 1st of January will be used if only Year is available, as defined below.

Reported Date (from the eCRF)	Analysis Date (Derived)
--/MM/YYYY	01/MM/YYYY
--/--/YYYY	01/01/YYYY
DD/--/----, or --/MM/----, or --/--/----	No imputation

7.10.3 Outliers

All values will be included in the analyses.

7.10.4 Visit Windows

Labs, vital signs, weight, PE, urine pregnancy test and ECG will be analyzed based on the following visit window.

Visit (study day)	Lab, Vital signs, PE	Weight, Urine Pregnancy Test	ECG
Baseline (1)	<= 1	<= 1	<= 1
Week 3 (15)	>=2 - <22	NA	NA
Week 5 (29)	>=22 - < 43	>=22 - < 43	NA
Week 9 (57)	>=43 - <71	>=43 - <71	NA
Week 13 (85)	>=71 - <99	>=71 - <99	CRF visit
Week 17 (113)	>=99 - <127	>=99 - <127	NA
Week 21 (141)	>=127 - <155	>=127 - <155	NA
Week 25 (169)	>=155 - <183	>=155 - <183	NA
Week 29 (197)	>=183 - <211	>=183 - <211	NA
Week 33 (225)	>=211 - <239	>=211 - <239	NA
Week x (7*x -6) (x is every 4 weeks after week 5)	>=7*x-20 - <7*x+8	>=7*x-20 - <7*x+8	NA
Final	Last Value within 7 days of last dose of study drug	Last Value within 7 days of last dose of study drug	Last Value within 7 days of last dose of study drug

8 DOCUMENT REVISION HISTORY

Version	Change
1	
Finalized before protocol amendment but never signed.
 
Document was finalized after protocol amendment and fully approved on the 22OCT2015 as verion 2.0 when it should be version 1.0.
 
Additional note to document this has been archived in the study TMF.

2	
Updated section 7.10.3 visit window.
 
Footnote of Schedule of Assessment table was updated based on protocol v3.0.
 
Section 7.5.4 was removed.
 
Added more analysis details to sections 7.6, 7.7 and 7.8.
 
Updated section 7.10.1.
 
[REDACTED]
 
[REDACTED]
 
Added viral /non-viral medical history to subgroup analysis section 7.8
 
[REDACTED]

	
Updated the list of Abbreviations.
 
Added sections 6.2.1, 6.2.2, 6.2.3 and 6.2.4 to describe AE, labs, vital signs, and ECG respectively.
 
Added section 6.2.5 for ECOG, and section 6.5 for previous and concomitant medications.
 
Used the population “All Randomized Subjects” instead of “FAS” to summarize subject disposition (section 7.2.1).
 
Added sensistivity analyses for efficacy endpoints when needed (section 7.4).

Version	Change
	[REDACTED]
	[REDACTED]
	[REDACTED]
	[REDACTED]
	Specified the populations for efficacy and safety analyses.
	Changed to use standard term “withdrawl of treatment” instead of “permanent discontinuation of study drug” for AE analysis (section 7.5.1).
	Added summary shifts to replace shift tables for abnormalities by reference range, and updated analysis: Shift table for highest CTCAE grade urinalysis and urinalysis by CTCAE will not be provided (section 7.5.2).
	Added the details for LFT changes, study drug dosing should be interrupted (section 7.5.2.1).
	Added the descriptions for continuous ECG parameters (section 7.5.4).
	[REDACTED]
	[REDACTED]
	More subgroups were added for subgroup analysis and updated the subgroups categories (section 7.8).
	Updated the definition for AR+ (section 7.8).
	Updated the description for interim analysis (section 7.9).
	Added section 7.10.2 for the imputation rule to calculate the time from initial diagnosis.

10 APPENDICES

10.1 Appendix 1: Definition of Efficacy Endpoints

10.1.1 Overall Survival

Overall survival is defined as the time from the date of randomization until the documented date of death from any cause.

Subjects who are still alive at the time of the data cutoff date will be censored on the last date known to be alive or at the data cutoff date, whichever occurs first.

10.1.2 Progression-Free Survival

Progression-free survival (PFS) is defined as the time interval from the date of randomization to the date of disease progression as determined by the investigator using RECIST 1.1 or the date of on-study death due to any cause, whichever occurs first. Please refer to section 7.4.2

Patients who die after receiving the first dose of enzalutamide without postbaseline tumor assessments evaluable using RECIST 1.1, will be considered to have a PFS event on the date of death.

The censoring rules for the primary and sensitivity analyses of PFS are summarized in the following table. The earliest of the following censoring times will be used:

Analysis	Censoring Rules	Date of Censoring
Primary analysis of PFS	No evaluable post-baseline imaging assessments, nor death	Date of randomization
	No radiographical progression nor death before analysis cutoff date	Date of last radiological assessment before analysis cutoff date
	No radiographical progression nor death before new HCC treatment	Date of last radiological assessment before start of new HCC treatment

10.1.3

[REDACTED]	[REDACTED]	[REDACTED]
[REDACTED]	[REDACTED]	[REDACTED]
	[REDACTED]	[REDACTED]
	[REDACTED]	[REDACTED]

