Status, EOT = end of treatment, FSH = follicle-stimulating hormone, FU = follow-up, HBV = hepatitis B virus, HCV = hepatitis C virus, N/A = not applicable, OPT = optional, PGx = pharmacogenomics, Q = every, SOC = standard of care

1. Phone call may be conducted if subject is unable to travel. Long-term follow-up will occur for up to 2 years, until death or subject withdraws consent or final analysis.
2. Medications taken within 14 days before the Screening visit and up to the 30-day Follow-up Visit will be collected.
3. HBV/HCV status will be assessed at Screening. HBV should be assessed using an assay for hepatitis B surface antigen. HCV testing should be performed using an antiHCV antibody assay (enzyme immunoassay [EIA] or enhanced chemiluminescence immunoassay [CIA]).
4. Computed tomography (CT)/magnetic resonance imaging (MRI) of the chest/abdomen/pelvis as well as any other anatomical region appropriate for the subject's disease must be performed within 28 days prior to day 1. Results from CT/MRI assessments performed prior to consent and within 28 days of day 1 may be used for Screening if available. Subsequent scans will be done every 8 weeks (+/- 7days) from Day 1 until treatment discontinuation criterion is met. To ensure comparability, the Screening and subsequent assessment should be performed using identical techniques.
5. Adverse events will be collected from the time of informed consent through the 30-day Follow-up Visit or through the day prior to the initiation of new antineoplastic treatment or investigational agent, or whichever comes first.
6. Clinical laboratory assessments include hematology, chemistry, coagulation, viral load (if applicable), pregnancy and urinalysis (urine dipstick). Lab parameters to be analyzed are listed under Appendix 12.8 Laboratory Assessments.
7. FSH testing is also required for postmenopausal women who are < 55 years of age at Screening.
8. Day 1 clinical laboratory tests do not need to be repeated if Screening labs were performed within 7 days prior to Day 1.
9. Urine pregnancy test will be performed in women of childbearing potential. Testing at treatment visits must occur prior to study drug administration.

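### SAP 10.1.2 gives a subject with no post-baseline scan who starts new HCC treatment and later dies two PFS statuses, with no precedence between them

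*SAP*

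**What the plan says.** SAP 10.1.2 defines PFS from randomization to investigator-assessed progression or on-study death, whichever is first, and then gives two sets of rules.

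- **Death sentence.** A subject who dies after the first dose of enzalutamide, with no evaluable post-baseline tumor assessment, "will be considered to have a PFS event on the date of death". It does not mention new treatment or placebo.
- **Censoring table.** It opens with "The earliest of the following censoring times will be used".
  - Row 1, "No evaluable post-baseline imaging assessments, nor death": censor at randomization.
  - Row 2, "No radiographical progression nor death before analysis cutoff date": censor at "Date of last radiological assessment before analysis cutoff date".
  - Row 3, "No radiographical progression nor death before new HCC treatment": censor at "Date of last radiological assessment before start of new HCC treatment".

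SAP 7.4.2, to which 10.1.2 refers, censors subjects who start another anti-tumor therapy before documented progression or death. The date is the last scan showing no progression. It also censors at day 1 anyone with no valid post-baseline assessment, and makes no exception for death.

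The baseline scan "must be performed within 28 days prior to day 1" (SAP 2, footnote 4 to the schedule). Protocol 4.5 randomizes on Day 1. Protocol 7.4.2 censors at the last scan and leaves detailed rules to the SAP.

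**The concern.** The main problem is the subject with no evaluable post-baseline scan who starts new HCC treatment and then dies. Row 3 asks only that there was no progression or death before the new treatment, so a later death does not switch it off. The death sentence applies to the same subject. The earliest-date instruction ranks censoring times against each other; it does not rank a censoring time against an event.

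If the death counts, time survived on the next therapy is credited as progression-free time. A comparable subject with one clean scan is censored before that therapy.

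The lesser problem is that row 1 says post-baseline and rows 2 and 3 do not. For some subjects with only a baseline scan, the earliest date therefore precedes time zero.

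PFS is the only secondary efficacy endpoint that can be read in the public documents. OS, the primary endpoint, is not touched.

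**Working it through.** **Plan's own figure.** The documents give no sizing figure for PFS. The OS figure is context only and reproduces: (1.2816 + 0.8416)² / [(2/9) × (ln 0.65)²] = 4.508 / 0.04124 = 109.3 events, against 109 stated (79.9% power at 109).

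**Rules applied literally.** Day 0 is randomization. Every table row whose condition is met is applied, and then the earliest date is taken.

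| Record | Table rows met | Table result | Other text |
|---|---|---|---|
| A. Baseline scan day −28, alive at cutoff | row 1: 0; row 2: −28 | censored at −28 | 7.4.2: day 1 |
| B. Baseline scan day −14, new treatment day 40, alive | row 1: 0; row 2: −14; row 3: −14 | censored at −14 | 7.4.2: day 1 |
| C. Baseline scan day −14, new treatment day 40, death day 120 | row 3: −14 | censored at −14 | death sentence: event at day 120; 7.4.2: censored |
| D. Scan day 56, new treatment day 70, death day 120 | row 3: 56 | censored at 56 | 7.4.2 agrees; death sentence does not apply |
| E. Baseline scan only, death day 40, no new treatment | none | none | death sentence: event at day 40; 7.4.2: censored at day 1 |

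Record C is the contradiction. On placebo the death sentence does not literally apply, but the general PFS definition still makes an on-study death an event against row 3. Record A gives −1 instead of −28 if the scan was on day −1, so the literal range is −28 to −1 days. Record E shows a related clash between 7.4.2 and 10.1.2.

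**Effect of the negative date.** In one simulated trial (110 and 55 subjects), 10 subjects were censored at day 0, censored at day −28, or dropped. The log-rank chi-square was 1.842 each time, because a subject censored at or before time zero is never in a risk set. Keeping the same 10 as events gave 1.294. So the choice between event and censoring can change the result; the choice between day 0 and day −28 cannot.

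**Number of record-C subjects.** No rates are given, so these are assumptions: 10% to 20% have no post-baseline scan, and 20% to 30% of those start new therapy. If the share who have died is 109/165 = 0.66:

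- low: 165 × 0.10 × 0.20 × 0.66 = 2.2
- high: 165 × 0.20 × 0.30 × 0.66 = 6.5

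A simulation (400 runs per setting, n = 165, exponential times, median PFS about 2.8 months, median OS 9.3 months, 8-week scans) gave means across four settings in these ranges:

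| Conflicted subjects | 6-month PFS, censored at randomization | 6-month PFS, event at death | Difference (points) |
|---|---|---|---|
| 2.0 | 18.1% | 18.6% | 0.5 |
| 3.1 | 19.4% | 20.2% | 0.8 |
| 4.5 | 18.9% | 20.0% | 1.1 |
| 5.9 | 20.0% | 21.5% | 1.5 |

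This is about a quarter of a point per conflicted subject (0.5/2.0 and 1.5/5.9).

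**The case against.** The strongest reply is that the intention is plain. Row 1 and the day-1 sentence in 7.4.2 both place the subject without a post-baseline scan at time zero, and PFS is defined as time from randomization. A negative date arises only by setting a general row against a specific one, and a programmer would probably floor it at zero. This stands: the negative date is a wording fault with no effect on the estimates.

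For record C, row 3 and both 7.4.2 rules point to censoring; only the death sentence disagrees. That is a good reason to resolve it as censoring, but it is not a stated precedence. The word on-study does not settle it either. The documents do not define it, and Protocol 5.3.1.1 follows survival and subsequent therapies for up to 2 years, so such deaths will be in the data.

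The assumed rates are open to challenge. Protocol 1.4 says no treatment is approved in this setting, and the first on-study scan is due at week 8. New therapy before any scan in 20% to 30% of unscanned subjects may be too high.

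Three stronger readings are tempting, and the documents do not support them:

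- **Every subject with only a baseline scan gets a time before randomization.** Record E meets no table row.
- **Randomized subjects leave the analysis.** The table censors them, and SAP 5.1 keeps all randomized subjects in the FAS. Dropping a negative time would be software behavior, not a rule of the plan.
- **Anyone who starts new therapy and then dies is in conflict.** With a post-baseline scan, row 3 and 7.4.2 agree (record D).

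**Conclusion.** The contradiction is real but narrow. A dosed subject with no evaluable post-baseline scan who starts new HCC treatment and later dies on study is censored by row 3 and SAP 7.4.2, and is an event by the death sentence (by the general PFS definition on placebo). No order is stated.

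The count is not in the documents. Under the assumed rates it is about 2 to 6 of 165, and 6-month PFS is about 0.5 to 1.5 points higher if the deaths count. A reader might infer a biased treatment comparison. That would need new-therapy use before the first scan to differ by arm, and nothing in the documents shows that it does.

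The pre-randomization date applies to subjects with only a baseline scan who are alive at cutoff or who started new HCC treatment. It affects the validity of the time value and possibly the reported counts, nothing more. This is a wording correction of low severity on a secondary endpoint.

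**What to change.** 1. In rows 2 and 3 of the 10.1.2 table, and in the matching censoring date in 7.4.2, use: *last evaluable post-baseline radiological assessment showing no progression; if none, date of randomization*. In row 3 keep the limit to scans before the new treatment. The earliest date can then never precede time zero.
2. Reword the death sentence to refer to study drug in both arms, and add: *provided no new HCC treatment was started before death; otherwise censor at the date of randomization*. This follows the plan's own censoring at new therapy. Step 1 alone would not settle record C.
3. Reconcile the day-1 sentence in 7.4.2 with the death rule, for example by giving it the exception for death that row 1 already has, so that one precedence holds in both sections.

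The cost is a few lines of SAP text and a small change to the PFS derivation; a few late deaths stop being PFS events. Protocol 12.9 shows that the primary analysis has already been done. The sponsor should therefore also confirm which rule was programmed and, where it departs from the SAP, justify that in the study report, as SAP 1 requires.
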